13.1 Study Design, Objectives and Endpoints

The goal of this phase II study is to estimate the probability of response after treatment of exemestane in post-menopausal women with advanced non-small cell lung cancer progressing while on immune checkpoint blockade. The primary endpoint of treatment response will be assessed at 6 weeks after the start of treatment using RECIST criteria. Secondary endpoints include the proportion of toxicities through 30 days after the last dose or start of new treatment as described in Section 10.2.2, disease-control as measured by response duration, progression-free and overall survival through 12 months from study enrollment and quality of life scores as measured by PROMIS-29 at baseline, every 3 weeks during treatment and at the end of treatment visit. The primary endpoint of response will be evaluated using a two-stage design.

Stage 1 will enroll 10 patients. If 2 or more patients have an objective response after completion of stage 1, an additional 19 patients will be enrolled in stage 2 for a total of 29 patients. If the total number of patients responding is 4 or greater, the treatment will be considered worthy of further investigation.

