This is a phase II study of daily oral exemestane for the treatment of advanced non-small cell lung cancer in post-menopausal women who are progressing on an FDA approved immune checkpoint blockade therapy. The study will be conducted using Simon's two-stage design.³⁰ Stage 1 will enroll 10 patients. If at least 2 objective responses are observed at the first disease re-evaluation at 6 weeks after beginning oral exemestane, Stage 2 will be activated. In Stage 2, an additional 19 patients will be enrolled for a total of 29 patients. If 4 or more objective responses are observed in the 29 patients, exemestane will be deemed worthy of further investigation in this patient population.

4 Patient Selection

Study entry is open to post-menopausal women regardless of race or ethnic background. While there will be every effort to seek out and include minority women, the patient population is expected to be similar to that of advanced non-small cell cancer lung studies at the University Of Minnesota. Men are not eligible for this study as exemestane works by suppressing estrogen production. Women of child-bearing potential are not eligible as exemestane is FDA pregnancy category X – known harm to the unborn.

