Note: Study visits are scheduled every 3 weeks independent of the immune checkpoint blockade therapy administration per standard of care. During exemestane a ± 2 day window is permitted for every 3 week visits (start of new treatment cycle) and a ± 7 day window is permitted for the every 6 week disease reassessment. The end of treatment (EOT) visit 30 days after the last dose of study drug may be performed with a ± 7 day window. Follow-up visits are per standard of care with disease status and survival status abstracted from the medical record.

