9.1 Schedule of Patient Tests and Procedures

	Baseline (within 14 days of enrollment)	During Exemestane Therapy		End of Treatment Visit 4 weeks \pm 1 week) after final dose of exemestane	Follow-up	
		Every 3 weeks (\pm 2 days)	Every 6 weeks (\pm 1 week)		disease response (until PD or start of new therapy)	survival at 1 year (all patients)
ASSESSMENTS						
Witten consent	X					
Medical history	X	X		X		
Review of prior anti-cancer therapy	X					
Concomitant meds	X	X				
Physical exam	X	X				
Vital Signs	X	X				
Weight	X	X				
ECOG Performance status	X	X				
Disease re-assessment			X		X	
Symptom and toxicity notation (pt diary)	X	X		X		
LABORATORY EVALUATIONS						
CBC/diff, plts	X	X				
Comprehensive Metabolic Profile (CMP)	X	X				
Estradiol assay ²	X					
SCANS AND PROCEDURES						
CT of chest/abd/pelvis	X ¹		X	X (if not done in previous 6 weeks)	X ⁴	
MRI or CT of brain if previous hx of CNS dz or as clinically indicated	X ¹					
DEXA scan	X ¹ (perform only if none in previous 12 months)	repeat every 12 months				
CONTINUATION OF STANDARD OF CARE IMMUNE CHECKPOINT INHIBITOR THERAPY						
Nivolumab pembrolizumab, or atezolizumab	Continue per SOC while maintaining every 3 week visits for exemestane					
RESEARCH RELATED						
Exemestane		25 mg po once a day every day				
Research staff "check-in" ³		Cycle 1 only between Day 8 and 12				
Reconciling of Exemestane tablets		X		X		
Quality of Life Questionnaire (PROMIS-29 Profile)	X	X		X		
Monitoring for stopping rule events		Refer to Section 10.3				
Blood Samples 30 ml serum (red top) 20 ml EDTA (purple top) 20 ml cell-free DNA BCT tube	X	X prior to cycle 2, 3, and 5		X		
Blood Samples 10 mL green top tube for PBMC	X	X prior to Cycle 2 and 3				
biopsy material ⁵	X	at the time of biopsy for clinical reasons				

1 Within 4 weeks of study enrollment

2 For women < 55 years of age

- 3 A member of the research staff will contact the patient to see how things are going (screen for toxicity) and if they have any questions
- 4 Per standard of care for patients who discontinued exemestane for reasons other than disease progression – abstract results from medical record
- 5 At enrollment archived from original diagnosis will request 15 unstained slides but require a minimum of 5 unstained slides for eligibility or resection and fresh at any time tissue is obtained for clinical reasons (i.e. SOC) - consent for tissue is embedded in the treatment consent

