12.1 Primary Endpoint

Initial disease response will be assessed 6 weeks after the start of exemestane using the Response Criteria in Solid Tumors (RECIST). Refer to Appendix II.

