13.2 Sample Size

Sample size is based on testing our primary endpoint using Simon's optimal two stage design with a type I error of 5% and power of 80%.³⁰ Our null hypothesis is that the response is $\leq 5\%$ (as all will be progressing on anti-PD1 therapy) and our alternative hypothesis is that response is $\geq 20\%$. If the treatment is truly not effective, there is a 5% chance of concluding that the drug is effective while if the treatment is truly effective, there is a 20% chance of concluding that it is not effective. Up to 10 patients will be enrolled per year.

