Progressive Disease (PD): At least a 20% increase in the sum of the diameters of target lesions, taking as reference the smallest sum on study (this includes the baseline sum if that is the smallest on study). In addition to the relative increase of 20%, the sum must also demonstrate an absolute increase of at least 5 mm. (Note: the appearance of one or more new lesions is also considered progressions).

Stable Disease (SD): Neither sufficient shrinkage to qualify for PR nor sufficient increase to qualify for PD, taking as reference the smallest sum diameters while on study

Evaluation of Non-Target Lesions

Complete Response (CR): Disappearance of all non-target lesions and normalization of tumor marker level. All lymph nodes must be non-pathological in size (<10 mm short axis)

Note: If tumor markers are initially above the upper normal limit, they must normalize for a patient to be considered in complete clinical response.

Non-CR/Non-PD: Persistence of one or more non-target lesion(s) and/or maintenance of tumor marker level above the normal limits

Progressive Disease (PD): Appearance of one or more new lesions and/or *unequivocal progression* of existing non-target lesions. *Unequivocal progression* should not normally trump target lesion status. It must be representative of overall disease status change, not a single lesion increase.

Although a clear progression of "non-target" lesions only is exceptional, the opinion of the treating physician should prevail in such circumstances, and the progression status should be confirmed at a later time by the review panel (or Principal Investigator).

Evaluation of Best Overall Response

The best overall response is the best response recorded from the start of the treatment until disease progression/recurrence (taking as reference for progressive disease the smallest measurements recorded since the treatment started). The patient's best response assignment will depend on the achievement of both measurement and confirmation criteria.

For Patients with Measurable Disease (i.e., Target Disease)

Target Lesions	Non-Target Lesions	New Lesions	Overall Response	Best Overall Response when Confirmation is Required*
CR	CR	No	CR	>4 wks. Confirmation**
CR	Non-CR/Non-PD	No	PR	>4 wks. Confirmation**
CR	Not evaluated	No	PR	
PR	Non-CR/Non-PD/not evaluated	No	PR	
SD	Non-CR/Non-PD/not evaluated	No	SD	documented at least once >4 wks. from baseline**
PD	Any	Yes or No	PD	no prior SD, PR or CR
Any	PD***	Yes or No	PD	

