Any	Any	Yes	PD	

* See RECIST 1.1 manuscript for further details on what is evidence of a new lesion.
 ** Only for non-randomized trials with response as primary endpoint.
 *** In exceptional circumstances, unequivocal progression in non-target lesions may be accepted as disease progression.

Note: Patients with a global deterioration of health status requiring discontinuation of treatment without objective evidence of disease progression at that time should be reported as "*symptomatic deterioration*." Every effort should be made to document the objective progression even after discontinuation of treatment.

For Patients with Non-Measurable Disease (i.e., Non-Target Disease)

Non-Target Lesions	New Lesions	Overall Response
CR	No	CR
Non-CR/non-PD	No	Non-CR/non-PD*
Not all evaluated	No	not evaluated
Unequivocal PD	Yes or No	PD
Any	Yes	PD

* 'Non-CR/non-PD' is preferred over 'stable disease' for non-target disease since SD is increasingly used as an endpoint for assessment of efficacy in some trials so to assign this category when no lesions can be measured is not advised

Duration of Response

Duration of overall response: The duration of overall response is measured from the time measurement criteria are met for CR or PR (whichever is first recorded) until the first date that recurrent or progressive disease is objectively documented (taking as reference for progressive disease the smallest measurements recorded since the treatment started).

The duration of overall CR is measured from the time measurement criteria are first met for CR until the first date that progressive disease is objectively documented.

Duration of stable disease: Stable disease is measured from the start of the treatment until the criteria for progression are met, taking as reference the smallest measurements recorded since the treatment started, including the baseline measurements.

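### Does Appendix II's confirmation rule leave it open which patients count as responders for the primary endpoint?

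*Combined protocol and SAP*

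**What the plan says.** Three places in the body fix the time of the primary response.

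- Section 3 makes the stage 1 decision depend on a count at one scan: "If at least 2 objective responses are observed at the first disease re-evaluation at 6 weeks after beginning oral exemestane". The Synopsis also names the first re-evaluation.
- Section 12.1: "Initial disease response will be assessed 6 weeks after the start of exemestane using the Response Criteria in Solid Tumors (RECIST). Refer to Appendix II".
- Section 13.1: "The primary endpoint of treatment response will be assessed at 6 weeks after the start of treatment using RECIST criteria". It then gives the two cut-offs, 2 of 10 and 4 of 29. The 4-of-29 sentence repeats no time point.

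Appendix II reproduces general RECIST 1.1 guidance. Under its heading on best overall response it says that a patient's "best response assignment will depend on the achievement of both measurement and confirmation criteria". The table there carries an interval of more than 4 weeks for confirmation, with a footnote: "Only for non-randomized trials with response as primary endpoint". Section 8 refers to the same appendix for the full guidelines and links the primary endpoint to re-evaluation every 6 weeks.

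**The concern.** This is a single-arm trial with response as its primary endpoint, so it meets the condition in the footnote. Section 12.1 cites the appendix without restricting the reference to the CR and PR definitions. Read literally, the body counts a response at week 6, while the appendix counts it only once a scan more than 4 weeks later agrees. No section says which applies.

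Both cut-offs turn on single patients: 1 against 2 of 10, and 3 against 4 of 29. If the count sits exactly at a cut-off and one week-6 PR is not seen again at week 12, the two readings give opposite decisions. With no written rule, the choice could in principle be made after the scans are known.

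**Working it through.** **1. What each passage governs.**

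| Place | Subject | Time | Confirmation |
|---|---|---|---|
| Section 3, stage 1 rule | objective responses | first re-evaluation, 6 weeks | not mentioned |
| Section 12.1 | initial disease response | 6 weeks | not mentioned; refers to Appendix II |
| Section 13.1 | treatment response | 6 weeks | not mentioned |
| Section 13.1, 4-of-29 rule | patients responding | not repeated | not mentioned |
| Appendix II, CR and PR criteria for target lesions | response at an assessment | any | none |
| Appendix II, duration of response | start of response | when measurement criteria are met | none |
| Appendix II, best overall response | best response over treatment | start to progression | more than 4 weeks |

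Appendix II therefore separates a measured response from best overall response and puts confirmation only on the latter. Section 6.1 fits the single-scan reading: a patient is unevaluable and replaced if the first re-evaluation is missed, and nothing is said about a missing second scan, which a confirmed endpoint would need.

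The 4-week interval, and its link to the footnote, stand only in table rows. The table may be broken in the extracted text: the ordinary PR row shows no confirmation entry. I take the requirement as covering PR, which favors the concern.

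**2. The plan's own figure.** Inputs from Section 13.2: null 5%, alternative 20%, type I error 5%, power 80%, Simon optimal design. For a stage 1 cut-off c,

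P(success) = sum over x from c to 10 of P(X1 = x) × P(X2 ≥ 4 − x), with X1 ~ Bin(10, p) and X2 ~ Bin(19, p).

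A search for the smallest expected size under the null returns 10 + 19 = 29 with success at 4 or more, so N = 29 reproduces. That design continues on 1 or more of 10 (type I error 0.0468, power 0.8011). The printed rule continues on 2 or more of 10 and gives 0.0259 and 0.5963. That mismatch is a separate matter; the printed rule is used below.

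**3. One disputed patient, no assumption needed.** Exact (Clopper-Pearson) 95% intervals:

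- 4/29 = 13.8% (3.9% to 31.7%): worthy of further study
- 3/29 = 10.3% (2.2% to 27.4%): not

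**4. How often the readings would differ.** The documents give no confirmation rate, so assume that a share f of week-6 responses is confirmed, f = 0.9 or 0.8. Confirmed responders are a subset of week-6 responders, so the probability of different decisions is P(pass at p) − P(pass at f·p).

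| True week-6 rate | f | Stage 1 decisions differ | Final decisions differ |
|---|---|---|---|
| 20% | 0.9 | 0.6242 − 0.5608 = 6.3% | 0.5963 − 0.5213 = 7.5% |
| 20% | 0.8 | 0.6242 − 0.4920 = 13.2% | 0.5963 − 0.4386 = 15.8% |
| 5% | 0.9 | 0.0861 − 0.0717 = 1.4% | 0.0259 − 0.0185 = 0.7% |
| 5% | 0.8 | 0.0861 − 0.0582 = 2.8% | 0.0259 − 0.0127 = 1.3% |

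The stage 1 column applies only if someone sets aside the explicit wording of Section 3.

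**5. What a confirmed endpoint would cost.**

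- Power: 59.6% falls to 52.1% (f = 0.9) or 43.9% (f = 0.8), if 20% is the week-6 rate.
- Time: stage 1 waits about 6 more weeks for the next scan.
- Scan interval: Section 9 allows a window of 7 days either way on each reassessment. The gap runs from (84 − 7) − (42 + 7) = 28 days to (84 + 7) − (42 − 7) = 56 days, so more than 4 weeks is missed only when both windows are at their extremes.
- Missing scans: follow-up imaging is "Per standard of care for patients who discontinued exemestane for reasons other than disease progression". The end-of-treatment CT in Section 9.1 covers part of this gap, because it is done if none was taken in the previous 6 weeks.

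**The case for a change.** The case for a change is that the week-6 reading, though natural, is not written down as the only one. The reference to Appendix II is unrestricted, the footnote describes this kind of trial, Section 8 speaks of repeated assessment for the primary endpoint, and neither the stage 1 sentence nor the 4-of-29 sentence in Section 13.1 names a scan. Two careful analysts could count different patients, and one sentence would prevent it.

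Some of this stands: no passage expressly sets confirmation aside, and a decision at the margin could depend on it. Most of it does not carry further. The 4-of-29 sentence closes the paragraph after the one that defines the primary endpoint at 6 weeks, and it counts that endpoint. Section 8 reads as a scan schedule. Appendix II is general text that also covers CA-125, PSA and inflammatory breast disease, so the trial-specific sections would normally govern. A clarifying sentence would only record the reading that the body already gives.

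**Conclusion.** This is a gap that analysts fill sensibly. The primary response is CR or PR at the 6-week re-evaluation, unconfirmed, and the same count serves both cut-offs and the 95% confidence interval. Followed that way, the plan yields a valid estimate of what Section 12.1 calls initial response. Stage 1 is settled by Section 3; only the 4-of-29 sentence leaves any room.

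At worst, one patient separates 13.8% from 10.3% and reverses the conclusion. Under the assumed 80-90% confirmation, the final decision would differ in 15.8-7.5% of trials at a true rate of 20% and in 1.3-0.7% at 5%. These percentages rest on confirmation shares that the documents do not supply and on an analyst choosing the less natural reading.

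Requiring confirmation is a defensible alternative, but it is another endpoint. It delays stage 1 by about 6 weeks and, on the same assumption, lowers power from 59.6% to 43.9-52.1%. Reasonable statisticians would differ on that trade, and nothing in the documents shows that the 6-week choice is wrong. No change to the plan follows.

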FDA	Food and Drug Administration
ICB	immune checkpoint blockade
IRB	Institutional Review Board
MCC	Masonic Cancer Center
MDSC	myeloid derived suppressor cells
MNCCTN	Minnesota Cancer Clinical Trials Network
NSCLC	non-small cell lung cancer
OnCore	Online Enterprise Research Management Environment
OS	overall survival
PD	progressive disease
PFS	progression free survival
PR	partial response
RECIST	Response Evaluation Criteria in Solid Tumors
SAE	serious adverse event
SD	stable disease
SOC	standard of care

Synopsis

Phase II Trial of Exemestane in Previously Treated Post-Menopausal Women with Advanced Non-Small Cell Lung Cancer

Study Design:	
This is a phase II therapeutic study of adding exemestane therapy in post-menopausal women with advanced non-small cell lung cancer (NSCLC) who are progressing while on treatment with an immune checkpoint blockade antibody (pembrolizumab, atezolizumab, or nivolumab).
 
Enrollment will use a two-stage design. Stage 1 will enroll 10 patients. If at least 2 objective responses are observed at the first disease re-evaluation after beginning oral exemestane, Stage 2 will be activated. In Stage 2, an additional 19 patients will be enrolled for a total of 29 patients. If 4 or more objective responses are observed in the 29 patients, exemestane will be deemed worthy of further investigation in this population.

Primary Objective:	To determine a preliminary estimate of response of daily oral exemestane for the treatment of previously treated, advanced non-small cell lung cancer (NSCLC) in post-menopausal women receiving and progressing on immune checkpoint blockade (ICB) therapy.
Secondary Objectives:	
To determine the toxicity profile of daily exemestane in combination with immune checkpoint blockade therapy in this patient population.To estimate the disease control rate, progression-free survival (PFS), and overall survival (OS) of exemestane in this patient population through 1 year from study enrollment.To estimate quality of life during treatment and for 1 month after discontinuation.
Correlative Objectives:	
To conduct an exploratory biomarker correlative study of clinical outcome utilizing archived tumor tissue and serum collected at baseline and serially during therapy.To examine biomarkers in tissue post-treatment at the time of re-biopsy, if performed.To examine serum biomarkers of the peripheral immune response after aromatase inhibition.

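### The Stage 1 rule of at least 2 responses in 10 is not the Simon optimal rule (at least 1 in 10) and gives about 60% power, not the stated 80%

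*Combined protocol and SAP*

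**What the plan says.** Section 13.2 derives the sample size from Simon's optimal two-stage design, with a null response rate of at most 5% and an alternative of at least 20%. It states the error rates in words: "If the treatment is truly not effective, there is a 5% chance of concluding that the drug is effective", and "if the treatment is truly effective, there is a 20% chance of concluding that it is not effective".

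Section 13.1 sets the decision rule. Stage 1 enrols 10 patients, and the rule for going on is: "If 2 or more patients have an objective response after completion of stage 1, an additional 19 patients will be enrolled in stage 2", which makes 29 in total, and at least 4 responders among the 29 count as success.

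The same Stage 1 rule stands in Section 3 ("If at least 2 objective responses are observed at the first disease re-evaluation at 6 weeks after beginning oral exemestane, Stage 2 will be activated") and in the Synopsis ("If at least 2 objective responses are observed at the first disease re-evaluation after beginning oral exemestane, Stage 2 will be activated").

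The only loss of power that the plan acknowledges is at the end of Section 13.4.2. It is described as slight and attributed to the toxicity stopping rules.

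**The concern.** The three statements of the rule agree with each other but not with the error rates in Section 13.2. In a Simon design, the published Stage 1 bound r1 is usually the largest number of responses at which the trial stops, so the trial continues with r1 + 1 or more. Reading such a bound one step too high gives a stricter rule with the same sample sizes and the same final cut-off.

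A stricter Stage 1 rule costs power. If it is too strict, an agent with the targeted 20% response rate is often dropped after 10 patients, and nothing in Stage 2 can recover those cases. Stage 1 decides whether 19 of the 29 patients are ever enrolled.

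**Working it through.** **Inputs.** From Section 13.2: p0 = 0.05, p1 = 0.20, type I error 0.05, power 0.80. From Section 13.1: n1 = 10, n = 29 (19 in Stage 2), Stage 1 rule X1 ≥ 2, success at X1 + X2 ≥ 4.

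**Formula.** With a = the smallest number of Stage 1 responses that opens Stage 2,

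P(success | p) = Σ over x ≥ a of P(X1 = x) · P(X2 ≥ 4 − x), where X1 ~ Bin(10, p) and X2 ~ Bin(19, p).

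**Terms at p = 0.20**

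| Stage 1 responses x | P(X1 = x) | P(X2 ≥ 4 − x) | Product |
|---|---|---|---|
| 1 | 0.2684 | 0.7631 | 0.2048 |
| 2 | 0.3020 | 0.9171 | 0.2770 |
| 3 | 0.2013 | 0.9856 | 0.1984 |
| 4 or more | 0.1209 | 1 | 0.1209 |

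- Rule as written (a = 2): 0.2770 + 0.1984 + 0.1209 = **0.5963**. The stated 80% is not reproduced.
- Rule with a = 1: 0.5963 + 0.2048 = **0.8011**. The stated 80% is reproduced.

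**The same calculation at p = 0.05** gives a type I error of 0.0259 for a = 2. The x = 1 term is 0.3151 × 0.0665 = 0.0210, so a = 1 gives 0.0468 (computed from unrounded terms).

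**Side by side**

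| | As written (≥2/10, ≥4/29) | ≥1/10, ≥4/29 | Section 13.2 |
|---|---|---|---|
| Power at 20% | 59.6% | 80.1% | 80% |
| Type II error at 20% | 40.4% | 19.9% | 20% |
| Type I error at 5% | 2.6% | 4.7% | 5% |
| Stop after Stage 1, p = 20% | 37.6% | 10.7% | not given |
| Stop after Stage 1, p = 5% | 91.4% | 59.9% | not given |
| Expected N, p = 5% | 11.6 | 17.6 | not given |
| Expected N, p = 20% | 21.9 | 27.0 | not given |

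Expected N is 10 + 19 × P(Stage 2 opens). Under the null this is 10 + 19 × 0.0861 = 11.6 as written and 10 + 19 × 0.4013 = 17.6 with a = 1.

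**Can another final cut-off restore the power?** No. At p = 0.20, P(X1 ≥ 2) = 1 − 0.1074 − 0.2684 = 0.6242, and power cannot exceed this. With at least 2 of 10 required, a final cut-off of 3/29 gives 62.0% and 5/29 gives 53.5%.

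**Which design is optimal for the stated inputs?** An exhaustive search over total sample sizes up to 40, keeping designs with type I error ≤ 5% and power ≥ 80% and ranking them by expected N under p0, puts first: n1 = 10, continue with ≥1, n = 29, success with ≥4 (expected N 17.62). The next is n1 = 11, continue with ≥1, n = 28, success with ≥4 (expected N 18.33). The protocol's 10, 29 and 4 match the first exactly. Only the Stage 1 rule differs, by one.

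**Where does the written rule reach 80% power?** Power is 79.2% at a true rate of 27% and 81.2% at 28%. The crossing is at about 27.4%.

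**The case against.** The best defence is that the rule is given identically in three places, so it may be a deliberate choice of a stricter Stage 1 and not a slip. The documents do not show how it arose, so the off-by-one explanation remains an inference, though the exact match of the other three numbers makes it likely. Even if the rule is deliberate, Section 13.2 is then wrong on power, type II error and the optimal label. One side has to change.

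Two further points are fair. First, the type I discrepancy is conservative. 2.6% is below the 5% limit, and even the optimal rule gives 4.7% because the binomial is discrete, so the fault lies in the power. Second, correcting the rule costs more in trial conduct than the small edit suggests: under a 5% response rate the chance of opening Stage 2 rises from 8.6% to 40.1%.

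Two other defences do not hold. The slight power loss conceded in Section 13.4.2 comes from toxicity stopping, and a loss of about 20 points is not slight. The primary objective is worded as a preliminary estimate, but Sections 13.1 and 13.2 set a formal go/no-go rule with stated error rates.

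**Conclusion.** The concern holds. The written rule has 59.6% power at the targeted 20% response rate, against a stated 80%. It stops an agent with that response rate after 10 patients 37.6% of the time, against 10.7% under the design that Section 13.2 describes. The two rules part when Stage 1 ends with exactly one response, which has a probability of 26.8% at a 20% response rate. In that case the written rule stops the trial and the optimal design continues it.

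The figures assume exactly 10 and 29 evaluable patients and the same response definition at both looks. They leave out the toxicity stopping rules, which would lower power somewhat further under either version. This must be settled before the Stage 1 decision is taken.

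**What to change.** Reconcile the Stage 1 rule with Section 13.2 in one of two ways.

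1. **Correct the rule.** In the Synopsis, Section 3 and Section 13.1, require at least 1 objective response among the first 10 patients. Keep 29 patients and the final cut-off of 4. Section 13.2 then stands, with exact values of 80.1% power and 4.7% type I error.
2. **Keep the rule.** If the stricter Stage 1 is intended, restate Section 13.2 as about 60% power (type II error about 40%) and type I error about 2.6%, remove the optimal label, and give the reason for the stricter rule.

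The first option restores the power that the plan claims. The text change is small and the maximum sample size does not move. Expected sample size under the null rises from 11.6 to 17.6. When Stage 2 opens it adds 19 patients, which at the planned maximum of 10 per year is at least 19/10 = 1.9 years of accrual. The stated optimal design already carries that cost. The second option costs no patients, but it accepts missing an agent with a 20% response rate about two times in five.
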